4.6. Other Analyses

4.6.1. Subgroup analyses

No subgroup analyses are planned.

4.6.2. Other pharmacokinetic analyses

All other pharmacokinetic analyses will be performed on the Pharmacokinetic analysis set and will follow the IE strategies outlined for the secondary PK objective in section 1.1.

4.6.2.1. Dose proportionality assessment

Dose proportionality may be assessed following guidance from CPMS prior to final database lock.

Power Model

The analysis will be based on selected available PK parameters. No imputation will be done for missing PK parameters for any participant.

Endpoint / Variables
AUC _(0-t) and C _{max} , as the data permit, at first, second, and third dose, separately
Model Specification

 Power model $y = \alpha * dose^\beta$ 
where y denotes the PK parameter being analyzed and dose denotes the dose administered to a subject.
 Dose proportionality implies that $\beta = 1$ and will be assessed by estimating β along with its confidence interval by regressing the \log_e transformed PK parameter on the \log_e dose as shown below: $\log_e y = \log_e \alpha + \beta \log_e dose$
Model Checking & Diagnostics

 Distributional assumptions underlying the statistical analyses will be assessed by visual inspection of residual plots. Normality will be examined by normal probability plots, while homogeneity of variance will be assessed by plotting the residuals against the predicted values for the model. If there are any important departures from the distributional assumptions, alternative models may be explored using appropriately transformed data.
Model Results Presentation

- Estimates of slope β will be reported along with corresponding 90% CIs. If the CI contains 1 then we shall assume Dose Proportionality to hold.

ANOVA Method

If power model does not show dose proportionality, dose proportionality may be assessed by an analysis of variance (ANOVA) model.

PK parameters will be dose-normalised prior to \log_e -transformed by multiplying by reference dose / dose. Dose-normalised PK parameters will be analysed separately using a fixed effects ANOVA model for dose. Point estimates for the adjusted means on the \log_e scale, the mean difference between each dose (test) and the reference dose and associated 90% confidence interval will be constructed using the residual variance. The point estimate and confidence interval will then be exponentially back-transformed to obtain adjusted (least square) geometric means for each dose, and point estimates and associated 90% confidence intervals for the ratio test/reference. The reference dose will be chosen based on the lowest clinically relevant dose over which PK can be adequately described, with each other dose as the test doses in the construction of the ratio $\mu(\text{test})/\mu(\text{reference})$.

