4. STUDY DESIGN

4.1. Overall design

This is a Phase 2a POC, multi-center, randomized, double-blind (sponsor unblinded), placebo-controlled, adaptive clinical study to evaluate the antiviral effect, safety, tolerability and PK/PD of orally administered VH4524184 over 10 days in up to approximately 28 ART naïve adults with HIV-1 and detectable viremia.

This study will be conducted in 2 parts. In Part 1, 21 TN participants will be randomized to 1 of 3 cohorts. Within each cohort, 6 participants will receive VH4524184 and 1 will receive matching placebo **CCI**

Part 2 of the study is optional. The conduct of Part 2 is dependent on the informal interim evaluation of the exposure-antiviral response data from Part 1 using available preliminary clinical data from Part 1. Interim analysis of Part 1 will determine if evaluation of a fourth dose of VH4524184 would be informative to properly characterize the exposure-antiviral relationship. If evaluation of a fourth dose is needed, Part 2 will be conducted and will include 1 additional cohort in which up to 6 participants would receive VH4524184 and 1 would receive matching placebo. Part 2 may evaluate 1 additional dose, with the dose and frequency informed by PK/PD modelling of Part 1 data.

In both Part 1 and Part 2, each dose of VH4524184 will be evaluated as double-blind (Sponsor unblinded) monotherapy for 10 days (primary endpoint). On Day 10, participants will start open-label SOC ART that is selected by the investigator and locally sourced. Participants will be followed weekly through Day 38. **CCI**

[REDACTED]

[REDACTED]

All participants will be screened for eligibility preferably within approximately 7 to 14 days before being randomized into a 10-day study intervention period. The screening period may be extended to 28 days to allow, at a minimum, receipt of all screening results and/or to accommodate scheduling.

Following screening, the study requires a total of 9 in-clinic visits (5 in-clinic visits will occur in the Monotherapy Period; 4 in-clinic visits will occur in the Open Label Follow-up Period) and 3 virtual visits (3 virtual visits will occur in the Monotherapy Period; participant may choose to attend the visit in clinic and this is acceptable). **CCI**

[REDACTED]

[REDACTED]

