4.1.1. General Methodology

If participants prematurely discontinue the study for non-safety reasons, additional participants may be recruited with randomization and assignment to the same cohort (to ensure a minimum of 5 evaluable participants in each of cohorts 1, 2 and 3, and optional cohort 4) at the discretion of the Sponsor in consultation with the Investigator.

Participants will not be replaced if the reason for discontinuation is the original participant meeting stopping criteria. ‘Discontinuation’ of study intervention refers to any participant who has not received all planned doses of the study intervention. In rare instances, it may be necessary for a participant to permanently discontinue study intervention.

Data will be summarized by study intervention (VH4524184 or placebo) and dose level, unless otherwise specified. In other words, placebos from each dose level will be grouped collectively, while active participants from each dose level will be grouped separately. As such, if optional Part 2 is not used, the following groups will be summarized: VH184 [redacted], VH184 [redacted], VH184 [redacted], and PBO. If optional Part 2 is used, the following groups will be summarized: VH184 [redacted], VH184 [redacted], VH184 [redacted], VH184 Dose Level 4 (to be determined by interim analysis) and PBO.

Data will be summarized either by visit or separately for the monotherapy period and overall (i.e., monotherapy period + follow-up), as appropriate for each endpoint, unless otherwise specified.

It is anticipated that patient accrual will be spread thinly across centers and summaries of data by center are unlikely to be informative and will not, therefore, be provided.

Continuous and categorical variables will be summarized using the following descriptive statistics, unless otherwise specified:

- Continuous data: n (number of participants used for the summary), arithmetic mean, standard deviation (SD), median, interquartile range, minimum and maximum. For PK data, geometric mean, SD of log-transformed data and geometric %CV_b may also be used.
- Categorical data: number and percentage of participants

Confidence intervals will use 95% confidence levels unless otherwise specified.

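### The dose-proportionality rule in SAP 4.6.2.1 turns an imprecise slope estimate into a conclusion that proportionality holds

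*SAP*

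**What the plan says.** SAP section 4.6.2.1 makes the analysis optional: "Dose proportionality may be assessed following guidance from CPMS prior to final database lock". If it is run, AUC and Cmax at the first, second and third dose are each regressed on dose on the natural-log scale, and proportionality corresponds to a slope β of 1. The output is specified as "Estimates of slope β will be reported along with corresponding 90% CIs", followed directly by the decision rule: "If the CI contains 1 then we shall assume Dose Proportionality to hold".

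A second method follows only on failure: "If power model does not show dose proportionality, dose proportionality may be assessed by an analysis of variance (ANOVA) model". That ANOVA works on dose-normalised parameters and yields point estimates and "associated 90% confidence intervals for the ratio test/reference".

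The section gives no acceptance limits for β, no maximum CI width and no inconclusive outcome. Protocol section 4.1 sets the group size: "Within each cohort, 6 participants will receive VH4524184 and 1 will receive matching placebo". SAP section 4.1.1 allows replacement of participants "to ensure a minimum of 5 evaluable participants in each of cohorts 1, 2 and 3". SAP section 5 bases the sample size on feasibility, so no precision target for β exists.

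**The concern.** A two-sided 90% CI that contains 1 is the same event as a non-significant test of β = 1 at the 10% level. The plan treats that event as support for proportionality, which rewards imprecision. The noisier the data, the wider the interval and the more likely it is to cover 1. In the opposite direction, a very precise interval lying just off 1 would fail, although the departure might be of no practical interest.

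The sequence of methods adds to this. The ANOVA ratios would expose wide uncertainty between doses, but they are considered only after the power model fails. A noisy pass ends the planned sequence.

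If the analysis is run, the study report could say that proportionality holds when the data are merely inconclusive. No section links this rule to the choice of a Part 2 dose or to the exposure-response work, so the stake is the accuracy of that one statement.

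**Working it through.** The documents give no power, precision or limits for β, so there is no stated figure to reproduce. The check asks how often the rule would declare proportionality when it is false.

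**Inputs from the documents**
- Rule: 90% CI for β contains 1 (SAP 4.6.2.1).
- Three doses in Part 1 with 6 active participants each, 18 in all (Protocol 4.1).
- Minimum of 5 evaluable per cohort (SAP 4.1.1); taken as 5 active per dose, 15 in all.

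**Assumptions, because the doses are redacted and no variability is stated**
- Doses evenly spaced on the log scale, with highest-to-lowest ratio r = 4, 10 or 30.
- Between-participant CV of 20%, 30%, 50% or 70%.
- True slope 0.8 as an example of non-proportionality. At r = 4 the top dose then has 4^(0.8 − 1) = 0.76 of the dose-normalised exposure of the bottom dose.

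**Formulas**
- Residual SD on the log scale: σ = √ln(1 + CV²).
- Sum of squares of log dose with n per dose: Sxx = 2n(½ ln r)² = (n/2)(ln r)². For n = 6 this is 3(ln r)².
- SE(β) = σ/√Sxx, with df = 3n − 2. For n = 6, df = 16 and t(0.95; 16) = 1.746.
- P(CI contains 1) comes from the noncentral t distribution with noncentrality (β − 1)/SE(β).

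**Worked case: r = 4, CV 30%, n = 6**
- σ = √ln(1.09) = 0.294.
- Sxx = 3 × (1.386)² = 5.765, so SE(β) = 0.294/2.401 = 0.122.
- Typical CI half-width = 1.746 × 0.122 = 0.21.
- Noncentrality = −0.2/0.122 = −1.63, giving P(CI contains 1) = 0.53.

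**Probability that the rule declares proportionality when β = 0.8**

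| Dose range | n per dose | CV 20% | CV 30% | CV 50% | CV 70% |
|---|---|---|---|---|---|
| 4-fold | 6 | 0.25 | 0.53 | 0.74 | 0.81 |
| 10-fold | 6 | 0.01 | 0.17 | 0.51 | 0.67 |
| 30-fold | 6 | 0.00 | 0.01 | 0.23 | 0.44 |
| 4-fold | 5 | 0.33 | 0.59 | 0.77 | 0.83 |

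At β = 1 the probability is 0.90 in every cell, whatever the precision. Each row rises towards that ceiling as the CV grows.

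**What a pass would leave open.** The half-width multiplied by ln r equals 1.746σ/√3, so r cancels. With 6 per dose this is 0.200, 0.296, 0.476 and 0.637 at the four CVs. A typical interval centred exactly on 1 is therefore compatible with these top-versus-bottom dose-normalised exposure ratios:
- CV 20%: 0.82 to 1.22
- CV 30%: 0.74 to 1.34
- CV 50%: 0.62 to 1.61
- CV 70%: 0.53 to 1.89

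**What an equivalence rule would do.** Suppose the whole 90% CI had to lie within 1 + ln(0.80)/ln(r) to 1 + ln(1.25)/ln(r). These limits are illustrative and not in the documents. In simulation with β = 1 and 6 per dose, the rule passes about 21% of the time at CV 20%, 1% at CV 30% and 0% at CV 50%, the same for all three dose ranges.

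**The case against.** The strongest objection is about weight. The analysis is optional, sits among the other PK analyses, and serves no listed objective or endpoint. SAP 4.3.2.3 and 4.3.2.4 give Part 2 dose selection and PK/PD work to separate clinical pharmacology analyses. β and its CI are reported, PK parameters are summarised and plotted, and the SAP speaks of assuming proportionality, not of having shown it. All of this stands, and it is why the point is minor. It does not make the rule sound: a conclusion fixed in advance should not depend on the data being imprecise.

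A second objection is that proportionality is plausible. Protocol 2.2.1.1 reports dose-proportional increases in the first-in-human study, and Protocol 4.3 says exposures in the highest cohort here will be lower than those already observed. The value 0.8 is thus an illustration without support in the documents. That is fair. The same account also mentions no further rise in exposure beyond a redacted point, so proportionality over these doses cannot be taken as given.

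A third objection is that even log spacing is the least precise placement of three equal groups over a fixed range. If the middle dose approached either end, Sxx would near 4(ln r)², and the 4-fold row with 6 per dose would become 0.15/0.43/0.70/0.78. A fourth, log-evenly spaced cohort of 6 would give 0.20/0.49/0.72/0.80. The exposure-ratio ranges above also rest on three evenly spaced doses. These shifts are real but modest.

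Finally, the model may be fitted to as many as six parameter-by-dose combinations, and the probabilities above are per interval. A claim that all of them are proportional would be less likely than any single pass, by an amount that depends on their correlation.

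**Conclusion.** The concern holds. As written, the rule converts non-rejection of β = 1 into a positive conclusion, and nothing elsewhere in the SAP adds limits, a precision condition or an unconditional second analysis. This is certain from the text and does not depend on the assumed numbers.

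The practical size does depend on them. With a wide dose range and low CV the false-pass risk is negligible; with a narrow range or high CV it exceeds one half, and the redactions prevent narrowing this further. Since the analysis is optional and its consequence is one statement in the report, this is a point for the sponsor to consider and does not threaten the trial's main conclusions.

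**What to change.** In SAP 4.6.2.1:
- Delete the sentence that assumes proportionality when the CI contains 1.
- Report β, its 90% CI and the implied dose-normalised exposure ratio r^(β − 1) with its CI, where r is highest over lowest dose, and interpret them descriptively.
- State that a wide CI containing 1 is inconclusive.
- Remove the condition on the ANOVA; if proportionality is assessed at all, present both analyses.
- If a formal criterion is still wanted, require the whole CI to lie within a range fixed in advance and tied to r, with an explicit inconclusive outcome. The pass rates above show that 0.80 to 1.25 limits would seldom be met at this sample size, so descriptive reporting is the more realistic choice.

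The cost is a small change of SAP wording and, if the analysis is run, one more set of ANOVA results. No new data and no change to study conduct are needed. What is lost is a yes-or-no conclusion that these group sizes cannot reliably support.

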4.6.2.2. Estimation of Accumulation Ratios

Accumulation ratios may be estimated for C_{\max} following guidance from CPMS prior to final database lock. These are defined as the ratio of PK parameters from last administration to first administration on Day 1, as follows:

$$R(C_{\max}) = \frac{C_{\max} \text{ on Day of last administration}}{C_{\max} \text{ on Day 1}}$$

To estimate the accumulation ratios for each dose level, a mixed effects ANOVA model will be used on the \log_e -transformed C_{\max} . Participant will be treated as a random effect in the model, while day will be treated as fixed effect categorical variable. The Kenward & Roger (KR2) degrees of freedom approach will be used [Kenward & Roger, 2009]. The accumulation ratio will be estimated by calculating the ratio of the geometric least squares means of PK parameters between last administration (e.g. CCI) and first administration (Day 1) and the corresponding 90% CI. No imputation will be done for missing PK parameters.

Model assumptions for the analyses outlined in sections 4.6.2.1 and 4.6.2.2 will be examined by obtaining a normal probability plot of the residuals and a plot of the residuals versus the fitted values (i.e. checking the normality assumption and constant variance assumption of the model respectively) to gain confidence that the model assumptions are reasonable. If warranted, alternative models or data transformations may be explored.

4.7. Interim Analyses

An informal planned interim analysis will be conducted after all participants in Part 1 have completed their monotherapy period.

The planned interim analysis will evaluate the PK and pharmacodynamic (antiviral activity) of VH4524184 and inform the need for Part 2, as well as future clinical development of VH4524184.

CCI

Any safety outputs provided at the interim analysis will summarise data by dosing levels, with placebo participants grouped with active participants at the corresponding dose level. In other words, safety data summaries will be blinded to study intervention, but not to dose level. Any 'by visit' outputs could include data from the follow-up period, if available.

The tables, figures and listings that will be provided at the planned interim analysis are described in the OPS.

CCI

Additional interim analyses may be performed during the course of the study to inform internal decision-making activities and/or support regulatory requests. No changes to the conduct of the study will be implemented as a result of these analyses.

4.8. Final Analyses

The final EoS analysis will be conducted after the completion of the study (i.e., when all participants complete the follow-up period with the Day 38 visit) and final datasets authorization. At the EoS analysis all primary, secondary and tertiary objectives will be

evaluated with two exceptions: the analysis of (i) viral resistance and (ii) pharmacogenetics (if done), may be evaluated at a later stage and each of these outcomes will be reported separately.

4.9. Changes to Protocol Defined Analyses

There were no changes or deviations to the originally planned statistical analysis specified in the protocol (Dated: 29 September 2023).

5. SAMPLE SIZE DETERMINATION

The sample size is based on feasibility and no formal calculation of power or sample size has been performed.

Further details on sample size considerations are included in protocol section 9.5.1.

6. SUPPORTING DOCUMENTATION

6.1. Appendix 1 Study Population Analyses

Unless otherwise specified, the study population analyses will be based on the Safety Analysis Set.

Study population analyses including analyses of participant's disposition, protocol deviations, demographic and baseline characteristics, prior and concomitant medications, will be based on GSK Core Data Standards. Details of the planned displays are included in the OPS.

6.1.1. Participant Disposition

A summary of the number and percentage of participants who enrolled or failed screening will be provided. For screen failures, the number and percentage of participants overall and by screen failure reason will be also provided.

A summary of the number and percentage of participants who entered, completed, are ongoing or withdrew from study at each study period (i.e. Monotherapy, Follow-Up) will be provided. A participant will be considered to have completed the Monotherapy period if they have completed Day 10 visit and have not started SoC prior to Day 10. If a participant has started SoC treatment prior to Day 10 visit and has performed Day 10 visit, he/she will be classified as having 'Not Completed' the Monotherapy phase. A participant is considered to have entered the Follow-Up period if there is a recorded concomitant antiretroviral treatment start date.

A summary of the number and percentage of participants who completed the study as well as those who prematurely withdrew from study will be provided. Reasons for study

withdrawal will be summarized. A participant is considered to have completed the study if he/she has a “Completed” status in the Study Conclusion eCRF page.

A summary of study intervention status will be provided. This display will show the number and percentage of participants who have completed the scheduled study intervention or have discontinued study intervention prematurely, as well as primary reasons for discontinuation of study intervention.

The number and percentage of participants who withdrew from study due to an AE will be summarised by the outcome (fatal versus non-fatal) of the AE.

A listing of reasons for study withdrawal will be provided.

Participant-level disposition information will be available via RAPIDO DV.

6.1.2. Demographic and Baseline Characteristics

The demographic characteristics including age, gender, ethnicity, race, height/weight and BMI at baseline will be summarized with descriptive statistics. In addition, the following age categories will be summarized: 18-64, 65-84 and >=85 based on the Enrolled Analysis Set.

Demographic data will be listed.

Other baseline characteristics data such as medical history and CDC HIV-1 classification will be available at the participant-level via RAPIDO DV. Participant-level HIV-1 associated conditions and pregnancy data will also be available via RAPIDO DV.

6.1.3. Protocol Deviations

Important protocol deviations will be summarized and listed.

Protocol deviations will be tracked by the study team throughout the conduct of the study. These protocol deviations will be reviewed to identify those considered as important as follows:

- Data will be reviewed prior to unblinding and freezing the database to ensure all important deviations (where possible without knowing the study intervention details) are captured and categorised in the protocol deviations dataset.
- This dataset will be the basis for the summaries of important protocol deviations.

Participant-level protocol deviations which result in exclusion from the Per Protocol analysis set will be available via RAPIDO DV.

- Data will be reviewed prior to unblinding and freezing the database to ensure all deviations leading to analysis population exclusions are captured and categorised in the protocol deviations ADaM dataset (note these exclusions are not captured in the SDTM dataset).

6.1.4. Prior and Concomitant Medications

Prior and concomitant medications will be coded using both the GSK Drug and WHO Drug dictionaries. However, the listing of concomitant medications will be based on GSK Drug dictionary only.

6.1.5. Medical Conditions

Medical occurrences beginning after obtaining informed consent but before the start of study intervention will be recorded as medical history/current medical conditions, not as AEs, and will be available via RAPIDO DV.

6.2. Appendix 2 Data Derivations Rule

6.2.1. Criteria for Potential Clinical Importance

Reference ranges for all laboratory parameters collected throughout the study are provided by the laboratory. A laboratory value that is outside the reference range is considered either high abnormal (value above the upper limit of the reference range) or low abnormal (value below the lower limit of the reference range). A high or low abnormal laboratory value is not necessarily of clinical concern.

The Division of AIDS (DAIDS) grading for severity of laboratory toxicities and clinical adverse events, version 2.1, July 2017 will be used to assign grades to laboratory values as specified in the protocol.

In addition, the following criteria will be used to flag potential clinical importance:

ECG Parameter	Units	Clinical Concern Range	
		Lower	Upper
Absolute			
Absolute QTc Interval (QTcF)	msec	< 320	> 450 (Males) > 470 (Females)

Change from Baseline		
Increase from baseline QTc	Msec	> 60*

*On-treatment triplicate averaged QTcF value > 60 msec over baseline regardless of sex

Vital Sign Parameter	Units	Clinical Concern Range	
		Lower	Upper
Absolute			
Systolic Blood Pressure	mmHg	< 85	> 140
Diastolic Blood Pressure	mmHg	< 45	> 90
Heart Rate	bpm	< 45 (Males) < 50 (Females)	> 100

Note: PCI values for Respiratory Rate & Temperature are not applicable.

